6.3 Recommended

6.3 Graft Versus Host Disease Prophylaxis and Treatment

1. MMF

Both intravenous and oral doses of MMF will be calculated using adjusted ideal body weight. If actual body weight is less than ideal body weight, actual body weight will be used. All patients will initiate the intravenous formulation of MMF on the day of transplantation (Day 0), a minimum of 2 hours after the end of the stem cell infusion. MMF will be administered at 30mg/kg/day in two divided daily doses from day 0 until day 27. At day 27 the MMF will be tapered by 250mg to be off by Day 56. If patient does not develop evidence of GVH. The intravenous formulation will be administered until at least day 14 after transplant. MMF will be administered as a 2 hour IV infusion. MMF will be induced with 5% dextrose. When patients have recovered from radiation-induced gastroenteritis and are capable of taking the oral MMF, they will be converted at an oral to intravenous ratio of 1:1. This can be done because of the high bioavailability of MMF. The oral formulation of MMF is available in 250mg capsules. The prescribed dose will be rounded to the nearest dose possible with these capsules.

2. Cyclosporine

All patients will receive cyclosporine 3mg/kg/day IV or 12.5 mg/kg/day orally from day -1 until day 50. Dosing should be based on adjusted ideal body weight. If GVHD is absent, cyclosporine will then be tapered by 5% week until day 180 when the drug is discontinued. Cyclosporine whole blood levels will be monitored.

6.31 If moderate to severe graft-versus-host disease occurs (Grade II-IV), patients will be treated with the administration of higher doses of methylprednisolone, anti-thymocyte globulin, etc.

6.32 Graft-versus-host disease will be graded according to previously defined criteria (Appendix IV,V).

6.4 Supportive Care during Transplant

On the day of admission menstruating females will start Provera 10mg p.o. daily and Nystatin vaginal suppositories 1 b.i.d. In addition, all patients will start, levofloxacin 500mg/p.o or I/V q daily, Bactrim DS 1 tablet p.o. b.i.d. or IV will be started and continue until day -2.

Hyperalimentation will be given while patient is unable to eat.

It is recommended that platelet transfusions will be given to maintain platelet count greater than 20,000/ μ l at all times. Single donor platelets will be used with an attempt to use family members when possible. All platelets will be filtered to remove contaminated leukocytes which may harbor cytomegalovirus (CMV). Packed RBC transfusions will be used to keep the hemoglobin greater than 8.5gm/dl. All blood products will be irradiated with 2500cGy prior to transfusions.

The management of infections in these immunocompromised patients must by necessity be individualized, but the following general approach will be utilized. If a specific infection is documented, patients will be placed on specific anti-microbial agents to treat that infection. For temperatures greater than 38.5°C without an obvious source in patients with less than 1000granulocytes/l, cultures of blood will be obtained. Following this, a third generation cephalosporin will be used as initial empiric antibiotic coverage. For persistent or recurrent fevers an aminoglycoside and or ancef will be added. Prophylactic intravenous amphotericin B will be used and the dose can be increased as clinically indicated. If a specific organism or site of infection is identified after starting empiric antibiotic coverage, therapy will be changed as needed.

Rev. 11/8/01

While hospitalized, patients will have daily CBC's with platelet count, and SMA-7 (Na, K, C1, CO₂, BUN, creatinine, glucose). SMA12 (total protein, albumin, phosphatase, Ca, SGPT, SGOT, alkaline phosphatase, total bilirubin, cholesterol) determinations will be performed on Monday, Wednesday and Fridays and chest x-rays will be done weekly. CSA levels q Mon & Thurs, and CMV blood cultures q Mon & Thurs when WBC >2000.

7.0 TOXICITIES TO BE MONITORED AND DOSAGE MODIFICATIONS

7.1 Radiation toxicities: The short term complications of TBI are: a). nausea and vomiting. This problem will be managed symptomatically. b) Oral mucositis is expected in all patients. All patients will receive oral care with hydrogen peroxide and clotrimazole. Only sponge toothbrushes will be allowed. Pain will be managed with morphine and dilaudid, c) Temporary alopecia will also be expected in all patients. Long-term complications of TBI include: a) cataracts, these can be managed successfully in the same way as cataracts unrelated to radiation. b) Solid tumors have been seen following TBI. c) Radiation fibrosis of the lungs, d) hypothyroidism and patient will be required to take supplemental thyroid medication, e). Sterility.

7.2 Chemotherapy Toxicities:

7.2.1 Toxicities of VP-16

- a) VP-16 may cause nausea, vomiting lasting for a few hours.
- b). Occassionally VP16 can cause allergic reactions, hemorrhagic cystitis and hepatotoxicity.
- b) Can cause mucositis, and dermatitis.

7.2.2 Busulfan Toxicities are myelosuppression, pulmonary fibrosis, increased pigmentation, grand mal seizures and temporary or permanent alopecias have also been seen.

If 2 of first 6 patients develop grade 3 liver or lung toxicity related to the preparative regimen the Busulfan dose will be decreased to the equivalent of 9mg/kg of the oral dose and AUC range will be changed to 600-800.

If 2 of first 6 patients require ventilator support for mucositis the VP-16 will be omitted.

7.3 The dose of methotrexate will be modified for impaired liver function based on serum direct bilirubin as follows:

| Direct Bilirubin mg/dl | % MTX dose |
|------------------------|------------|
| ≤ 2 | 100% |
| 2.1 – 3.0 | 50% |
| > 3.0 | 0% |

7.4 The dose of cyclosporine and methotrexate will be modified for impaired renal function based on serum creatinine.

| Creatinine mg/dl | % CSA + MTX |
|------------------|-------------|
| < 1.5 | 100% |
| 1.6 – 1.7 | 75% |
| 1.8 – 2.0 | 50% |
| > 2.0 | 0% |

8.0 Toxicities will be graded per CTC 2.0 (Appendix VII) publish date April 30, 1999. Rev. 11/8/01

9.0 STUDY CALENDAR SEE APPENDIX VI.

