1.0 OBJECTIVES

1.1 To determine the efficacy of intravenous busulfan, dose targeted to achieve AUC of 700-900 combined with fractionated total body irradiation and VP16 as a preparative regimen for marrow transplantation from an HLA-identical sibling in patients with advanced hematological malignancies (AML or ALL) beyond 2nd remission, induction failure, in relapse, chronic myelogenous leukemia in blast crisis and myelodysplasia (RAEB and RAEBIT).

Rev. 6/13/02 1.2 To determine the efficacy of this regimen in patients with AML in first remission with unfavorable cytogenetics.

1.3 To evaluate the early and late toxicities of this regimen.

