
FTBI and VP-16 in an attempt to decrease the relapse rate in those patients transplanted for advanced hematological malignancies. The rationale behind the study was that we combined three non-cross resistant anti-leukemic agents with non-overlapping extramedullary toxicities. An in vitro synergy has been demonstrated between busulfan/VP-16 and busulfan/VP-16 has been proven to be an effective regimen for relapsed leukemia and for ABMT for AML in first and second remission.^{23,24} The dose limiting toxicity occurred at 12mg/kg the MTD was defined at 11mg/kg. At this dose level median first dose AUC for these patients was 892 μ M*min (460-1267). With a median follow-up of 11.5 months, the disease-free survival is 32%, and the probability of relapse is 40%. The only variable predictive of a disease-free survival and relapse was the busulfan dose of 7-8 mg/kg. In this phase I study there was a wide variability of the AUC of busulfan due to the variability of absorption of oral busulfan. An AUC of 700-950 showed a trend to a decreased relapse rate and improved disease free survival.

A phase II study utilizing IV busulfan was conducted at City of Hope which has resulted in FDA approval of IV busulfan and it is proposed to substitute IV busulfan which has been shown to have more predictable pharmacokinetic properties than the oral preparation resulting in a better toxicity profile.^(25,26,27)

Rev. 6/13/02

*Patients with AML in first complete remission (CR1) with unfavorable cytogenetics have a relapse rate of 40% with our current transplant regimen consisting of fractionated radiation and etoposide. We propose to use this new preparative regimen to see if it can improve the DFS and relapse rate for this subset of patients with AML in first CR.

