6.2 Preparative Chemotherapy Regimen

Rev. 8/12/02

* Patient to sign consent form before starting Dilantin.

Rev. 11/8/01

Friday/Day -18

Begin dilantin 300mg/p.o. t.i.d. times 1 day, then 300mg/p.o./IV daily times 14 days.

Tuesday/Day -14

Admission or outpatient, dilantin blood levels will be checked and dose adjusted as needed to meet therapeutic range. Further adjustments if clinically indicated. Busulfan test dose administered at 6 a.m. as a single dose. The I/V dose is calculated as follows:

1. Body surface area (BSA) is calculated by the equation:

$$\text{BSA} = \frac{(\text{Actual body wt.(kg)} \times \text{height (cm)})}{3600}$$

Rev. 6/13/02

2. 22mg/m² I/V Busulfan will be given over 2 hours. Blood levels will be obtained with the first dose as per appendix 1 and will be performed at City of Hope.

Rev. 11/8/01

Wednesday/Day -13

Busulfan AUC will be calculated by standard methods available in the City of Hope Analytical Pharmacology Core Facility (APCF). The resulting AUC will be used to determine the dose required to achieve an AUC of 800 $\mu\text{M}^* \text{min}$ according to the following formula:

$$\text{Adj dose} = \text{Current dose} \times \frac{800\mu\text{M}^* \text{ min}}{\text{test dose AUC}}$$

Rev. 6/13/02

The maximum dose given will not exceed 32mg/m². There is no limit on dose reduction Busulfan dose will only be adjusted for AUC's <700 or >900 $\mu\text{M}^* \text{min}$.

Thursday/Day -12

The adjusted dose Busulfan dose will be given at 6 a.m. and blood levels will be repeated. Further dose adjustments will be performed if AUC >1000.

Friday/Day -11

Patient admitted to BMT or receive further dose of Busulfan in clinic.

Busulfan dosing restarted at 6 p.m. and is repeated every 6 hours for a total of 14 doses.

Tuesday/Day -7

Fractionated TBI will be given at 120 cGy per fraction for a total of 4 days for a total of 10 fractions for a total dose of 1200 cGy. See Appendix II.

Saturday/Day -3

VP-16 30mg/kg based on adjusted ideal body weight will be administered.

Tuesday/Day 0

PSC reinfusion/or BM infusion

See Appendix 3 for PSC Collection

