12.0 STATISTICAL CONSIDERATIONS

- 12.1 Primary and Secondary Endpoints: The primary endpoint of the Phase II study is to evaluate the efficacy of FTBI/BU/VP-16 with a targeted Busulfan dose of AUC 700-900 as a preparative regimen for allogeneic BMT in patients with advanced hematological malignancies (AML or ALL beyond second remission, in induction

failure, or in relapse; CML in blast crisis; and myelodysplasia, RAEB and RAEBIT). Secondary endpoints will include early and late toxicities of this regimen.

Efficacy will be estimated based on 2 and 5 year disease-free survival (DFS). The effects of cytogenetics, WBC at presentation, and number of courses of induction therapy to achieve remission will be evaluated as possible prognostic factors for relapse, DFS, and overall survival.

- 12.2 Sample size Estimation and Length of Accrual: A total of 50 patients with advanced malignancies and less than 50 years old (physiological age) will be accrued to this trial, so that in estimating the engraftment and relapse rates the maximum standard error will be 0.7. We expect to accrue approximately 10-12 patients per year so that this trial will require 4-5 years of completion.
- 12.3 If at any time the severe treatment related complication rate (e.g. severe VOD, interstitial pneumonia, neurotoxicity at day 100 post BMT) or regimen related mortality exceeds 20% with a high probability (i.e. >95%) then further accrual to the trial will be terminated. This would occur if the following numbers of events have been observed, monitoring after every set of 10 patients is accrued:

| Number of Patients Accrued | Number of Events Leading to Early Termination |
|-------------------------------|--|
| 10 | 5 |
| 20 | 8 |
| 30 | 11 |
| 40 | 14 |

12.4 **Statistical Analyses:** The rate of engraftment and median time to engraftment will be estimated, defined as time to ANC > 500 and platelets >20,000.

The Kaplan-Meier method will be used to estimate time to relapse, DFS, and overall survival, and 95% confidence intervals will be calculated using Greenwood's variance.

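### After the early liver/lung toxicity trigger the busulfan AUC range moves to 600-800, but the 6.2 formula target of 800 and the 700/900 limits are not updated, which weakens the de-escalation

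*Combined protocol and SAP*

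**What the plan says.** Section 1.1 describes intravenous busulfan "dose targeted to achieve AUC of 700-900", and section 12.1 defines the regimen under test in the same terms, "with a targeted Busulfan dose of AUC 700-900 as a preparative regimen".

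Section 6.2 puts this into practice. A test dose of 22 mg/m2 is given on Day -14. On Day -13, "The resulting AUC will be used to determine the dose required to achieve an AUC of 800" (in µM*min), by multiplying the current dose by 800 and dividing by the test-dose AUC. The result is capped at 32 mg/m2, and "Busulfan dose will only be adjusted for AUC's <700 or >900". After the Day -12 dose, "Further dose adjustments will be performed if AUC >1000".

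Section 7.2.2 holds the rule for early toxicity. If two of the first six patients have grade 3 liver or lung toxicity attributed to the preparative regimen, "Busulfan dose will be decreased to the equivalent of 9mg/kg of the oral dose and AUC range will be changed to 600-800". It gives no new number for the formula, does not restate the 700/900 limits or the Day -12 limit of 1000, and gives no mg/m2 figure for the reduced intravenous dose. No other section supplies them.

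**The concern.** The number 800 sits in the centre of 700-900 and at the top of 600-800. If pharmacy staff go on using the printed formula after the trigger, every patient whose dose is adjusted is aimed at the ceiling of the safety range instead of its middle.

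This matters because 7.2.2 is the only rule that lowers busulfan exposure for later patients when liver or lung toxicity appears early. Section 12.3 can stop accrual, but it does not change the dose. The margin is also narrow: in the phase I study summarised in section 2.0, "The dose limiting toxicity occurred at 12mg/kg the MTD was defined at 11mg/kg". A de-escalation ordered after serious toxicity should not depend on what the person doing the calculation infers.

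**Working it through.** **Reproducing the plan's target.** The midpoint of the original range is (700 + 900)/2 = 800, which is the figure in the 6.2 formula. The midpoint of the new range is (600 + 800)/2 = 700.

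**What the formula does to a lower start.** Assume linear kinetics and write k for a patient's AUC per mg/m2.
- Test AUC = k × test dose.
- Adjusted dose = test dose × target / (k × test dose) = target / k.
- The test dose cancels. With target 800, a patient adjusted both before and after the trigger gets 800/k each time, a reduction of 0%. With target 700 the ratio is 700/800 = 0.875, a reduction of 12.5%. The 32 mg/m2 cap is the exception.

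**Who is affected.** The protocol does not give the intravenous equivalent of 9 mg/kg oral. Taking 22 mg/m2 to match the oral MTD of 11 mg/kg (an assumption), the reduced start is 22 × 9/11 = 18 mg/m2. With limits read as 600-800, the lower limit of 600 at 18 mg/m2 corresponds to 600 × 22/18 = 733 at 22 mg/m2, and the upper limit of 800 to 800 × 22/18 = 978. With target 800, ignoring the cap:

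| AUC at 22 mg/m2 | Before trigger | After trigger | Dose change |
|---|---|---|---|
| below 700 | raised to 800 | raised to 800 | none |
| 700 to 733 | left alone | 573-600 at 18 mg/m2, raised to 800 | higher |
| 733 to 900 | left alone | left at 18 mg/m2 | down 18% (1 - 18/22) |
| 900 to 978 | cut to 800 | left at 736-800 | down 0-8% |
| above 978 | cut to 800 | cut to 800 | none |

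For example, a patient with AUC 1000 at 22 mg/m2 gets 22 × 800/1000 = 17.6 mg/m2 before the trigger. Afterwards the test AUC at 18 mg/m2 is 1000 × 18/22 = 818, and the dose is 18 × 800/818 = 17.6 mg/m2 again. With target 700 it would be 22 × 700/1000 = 15.4 mg/m2.

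**Illustrative size.** The documents give no intravenous AUC distribution, so these inputs are assumed: lognormal AUC with median 700, 800, 892 or 1000 at 22 mg/m2, CV 20, 25 or 30%, cap 32 mg/m2, post-trigger start 18 mg/m2, and 1,000,000 draws for each of the 12 combinations. The comparison is with the pre-trigger rule.

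| After the trigger | Fall in mean AUC | Same dose as before | Dosed higher |
|---|---|---|---|
| limits 600-800, target 800 | 4.1-7.0% | 41-64% | 2.3-9.3% |
| limits 600-800, target 700 | 11.2-12.9% | 0-10% | 0% |

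If the 700/900 limits also stay as printed with target 800, the fall in mean AUC is -0.2 to 1.1%.

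**Chance that it arises.** P(at least 2 of 6) = 1 - (1-p)^6 - 6p(1-p)^5. This is 0.114, 0.345 and 0.580 at true rates of 10%, 20% and 30%. The rates are assumed, because the protocol states no expected rate.

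**The case against.** The strongest reply is that 7.2.2 is a later, conditional instruction that changes both dose and range. Sections 1.1 and 12.1 treat the range as the target, and 800 is merely its midpoint, so a sensible reader would move the formula constant along with the range. That is a fair reading, and no section says that 800 survives the trigger. But no section says 700 either, while 800 is printed in the formula. Two careful people could differ by 12.5% in dose for the same patient.

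The 4-7% figure also depends on a half-updated reading, in which staff move the limits but keep the target. Updating both gives 11-13%, and updating neither gives about 0%. This stands, and is why all three are shown.

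The upper tail is still protected when the limits move to 600-800. In the simulation above, patients with expected AUC over 800 fall from 13-23% before the trigger to 0% with either target. Adding an assumed 10% residual CV (median 800 or 892, between-patient CV 15-35%, start 18 mg/m2), delivered AUC above 900 occurs in 11-15% before the trigger, 5-7% after it with target 800, and 1-2% with target 700. So real protection remains, though less than the range implies.

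A reader might go further and infer that the de-escalation does nothing, or that most patients keep their old dose. The text does not support either. A simulation that keeps the start at 22 mg/m2 gives a fall of only 1.6-6.2% and an unchanged dose in 57-80% of patients, but 7.2.2 explicitly orders a dose decrease.

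Finally, the rule concerns only the first six patients. At the 10-12 patients a year expected in 12.2, six accrue in about 0.5-0.6 years, and the revision marks run to August 2002. The window may have passed, but the documents give neither an opening date nor the outcome in those patients.

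**Conclusion.** The inconsistency holds and should be fixed. After the trigger, the printed formula aims adjusted patients at the ceiling of the new range and cancels the ordered reduction for anyone adjusted both before and after. That part needs only the midpoint arithmetic and linear kinetics, and confidence in it is high. The de-escalation is weakened, not void, because patients left within range keep the lower dose.

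Confidence in the size is low. The loss of roughly half the intended fall in mean AUC, and the 2-9% of patients dosed higher than before, rest on an assumed AUC distribution, an assumed 18 mg/m2 start and limits read as 600-800. The point is conditional on the trigger firing.

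**What to change.** State in both 6.2 and 7.2.2 that after the trigger the formula target is 700 and the dose is adjusted for AUC below 600 or above 800. In the same amendment, give the reduced intravenous dose in mg/m2 and say whether the Day -12 limit of 1000 should come down. That limit was 100 above the old ceiling and is 200 above the new one; keeping the same gap would put it at 900.

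The cost is a short wording amendment, with no added patients or procedures. The clinical downside is lower busulfan exposure after the trigger. Section 2.0 reports that "An AUC of 700-950 showed a trend to a decreased relapse rate and improved disease free survival", so some anti-leukemic effect could be lost. Section 7.2.2 already accepts that trade by choosing 600-800. If the sponsor does want 800 kept as the target, the protocol should say so and give the reason.

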10.0 CRITERIA FOR EVALUATION AND DEFINITION

- 10.1 Achievement of a lymphohematopoietic graft is defined as recovery from post-transplant.
- 10.2 Complete remission is defined as attainment of M-1 marrow status, and no evidence of recurrent extramedullary disease.
- 10.3 Length of survival is measured from entry on study to death or time of last contact.
- 10.4 Treatment failure is defined as death from toxicities associated with transplant procedure or recurrence of malignancy.
- 10.5 All registered patients including those removed from the treatment protocol will be followed for survival every six months.

11.0 CRITERIA FOR REMOVAL FROM STUDY

There are two situations that will determine removal of a patient from the study:

- 11A. The patient may always be removed from the study whenever he/she wishes.
- 11B. If the scheduled bone marrow donor decides not to provide bone marrow.

12.0 STATISTICAL CONSIDERATIONS

- 12.1 Primary and Secondary Endpoints: The primary endpoint of the Phase II study is to evaluate the efficacy of FTBI/BU/VP-16 with a targeted Busulfan dose of AUC 700-900 as a preparative regimen for allogeneic BMT in patients with advanced hematological malignancies (AML or ALL beyond second remission, in induction

failure, or in relapse; CML in blast crisis; and myelodysplasia, RAEB and RAEBIT). Secondary endpoints will include early and late toxicities of this regimen.

Efficacy will be estimated based on 2 and 5 year disease-free survival (DFS). The effects of cytogenetics, WBC at presentation, and number of courses of induction therapy to achieve remission will be evaluated as possible prognostic factors for relapse, DFS, and overall survival.

- 12.2 Sample size Estimation and Length of Accrual: A total of 50 patients with advanced malignancies and less than 50 years old (physiological age) will be accrued to this trial, so that in estimating the engraftment and relapse rates the maximum standard error will be 0.7. We expect to accrue approximately 10-12 patients per year so that this trial will require 4-5 years of completion.
- 12.3 If at any time the severe treatment related complication rate (e.g. severe VOD, interstitial pneumonia, neurotoxicity at day 100 post BMT) or regimen related mortality exceeds 20% with a high probability (i.e. >95%) then further accrual to the trial will be terminated. This would occur if the following numbers of events have been observed, monitoring after every set of 10 patients is accrued:

| Number of Patients Accrued | Number of Events Leading to Early Termination |
|-------------------------------|--|
| 10 | 5 |
| 20 | 8 |
| 30 | 11 |
| 40 | 14 |

12.4 **Statistical Analyses:** The rate of engraftment and median time to engraftment will be estimated, defined as time to ANC > 500 and platelets >20,000.

The Kaplan-Meier method will be used to estimate time to relapse, DFS, and overall survival, and 95% confidence intervals will be calculated using Greenwood's variance.

The intent-to-treat group will include all patients receiving the preparative regimen for BMT. For overall survival, failure time will be calculated from the day of first treatment to the day of death due to any cause for those patients who fail. For DFS, the failure time will be calculated from the day of first treatment to the day of disease relapse or death due to any cause. For patients who remain alive and well at the time of analysis, the survival time will be censored as of the date of last contact. The Cox proportional hazard regression model will be used to analyze possible prognostic factors for relapse, DFS and overall survival.

Revised
9/26/00

12.5 Patients with AML with unfavorable cytogenetics will be a subset analysis that will include approximately 12 patients. This number is too small for formal hypothesis testing. It will give us some experience with this population of patients and descriptive analysis will be used along with estimation of relapse rate and 95% C.I.

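### The standard error of 0.7 that Section 12.2 gives as the reason for 50 patients is impossible for a proportion; the maximum at n = 50 is about 0.07

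*Combined protocol and SAP*

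**What the plan says.** Section 12.2 states that "A total of 50 patients with advanced malignancies and less than 50 years old (physiological age) will be accrued to this trial", and gives the reason: "so that in estimating the engraftment and relapse rates the maximum standard error will be 0.7". It gives no unit, formula or assumed rate, and no other section restates or corrects the figure.

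Section 12.1 bases efficacy on disease-free survival (DFS) at 2 and 5 years. For the analysis, Section 12.4 says that "The Kaplan-Meier method will be used to estimate time to relapse, DFS, and overall survival", with 95% confidence intervals from Greenwood's variance. For patients alive and well at the time of analysis, "the survival time will be censored as of the date of last contact". Section 12.4 defines failure times for overall survival and for DFS. It does not say how a death without relapse enters the time-to-relapse analysis.

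**The concern.** A standard error of 0.7 lies outside the possible range for a rate between 0 and 1. The trial is a single-arm estimation study, and Section 12 states no null rate, target rate or power. The precision statement is therefore the whole justification for 50 patients, and as printed it cannot be used to judge whether 50 is enough.

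There is a second, smaller point. Engraftment can be treated as a simple proportion, but time to relapse is to be estimated by Kaplan-Meier. If the printed value is changed to 0.07 with no qualification, it would still be offered as a maximum for the relapse rate, and that holds only under conditions the plan does not state.

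**Working it through.** **Inputs.** n = 50 and the printed maximum standard error (SE) of 0.7, both from 12.2. The word maximum implies p = 0.5, where p(1−p) is largest; the plan does not state p.

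**Attempt to reproduce 0.7.** For a proportion, SE = sqrt(p(1−p)/n).

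- At p = 0.5 and n = 50: sqrt(0.25/50) = 0.0707. The 95% half-width is 1.96 × 0.0707 = 0.139.
- Largest SE at any sample size (n = 1): sqrt(0.25/1) = 0.5.
- n that would give SE 0.7: 0.25/0.49 = 0.51, less than one patient.
- n that would give SE 0.07: 0.25/0.0049 = 51.0, in line with the planned 50.

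**Other readings tried.** None gives 0.7.

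| Reading | Value |
|---|---|
| Denominator n−1 = 49 | 0.0714 |
| n = 38 (the roughly 12 patients of 12.5 taken out of the 50) | 0.081 |
| n = 62 (those patients added to the 50) | 0.064 |
| 95% half-width | 0.139 |
| 95% full width | 0.277 |
| SE in percentage points | 7.07 |
| SE of the event count | 3.54 |

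Read as 0.7 percentage points, the figure would need 0.25/0.007² = about 5,102 patients.

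**Does 0.0707 also bound a Kaplan-Meier relapse estimate?** The plan gives no planning rates, so this is an illustration only. It uses the phase I oral-busulfan results in Section 2.0: probability of relapse 40%, DFS 32%. It assumes that deaths without relapse are censored, that the hazards of relapse and of such death are proportional, and that there is no other censoring.

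- Relapse share of the total hazard: ln(0.60)/ln(0.32) = 0.448.
- Greenwood SE: sqrt(0.60² × 0.448 × (1/0.32 − 1)/50) = 0.083. The half-width is 1.96 × 0.0828 = 0.162.
- Simulation of 40,000 trials of 50 patients on the same assumptions: empirical SE 0.0833, mean Greenwood SE 0.0817.

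If death without relapse is instead a competing event, with the same hazards and complete follow-up, the cumulative incidence of relapse is 0.448 × (1 − 0.32) = 0.305. Its SE is sqrt(0.305 × 0.695/50) = 0.065, below 0.0707.

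**The case against.** The strongest case on the other side accepts that 0.7 is impossible and disputes how much follows from it.

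- **It is an obvious slip with no consequences.** A statistical reader would see 0.07 at once, 50 patients agree with it, and no stopping rule, accrual figure or analysis uses it. This stands as a limit on the effect. It does not make the sentence usable, because the sentence is the only stated reason for the sample size.
- **A zero may have been lost in converting the PDF.** Digits are missing or altered elsewhere in the text, mostly in the dense toxicity tables. The prose of 12.2 is otherwise clean, but the possibility is real and the source page should be checked. If it reads 0.07, the numerical correction falls away and only the qualification remains.
- **The Kaplan-Meier point is separate and conditional.** Section 12.2 claims no precision for DFS. Death is an event for DFS, so only incomplete follow-up raises its standard error above the limit, and 10.5 and Appendix X provide continuing follow-up. This is fair: the excess is possible, not certain.
- **The 40% in Section 2.0 may be a cumulative incidence.** Then 40% relapse plus 28% death without relapse gives the 68% that matches DFS of 32%, and as a simple proportion the SE is sqrt(0.4 × 0.6/50) = 0.069. But 12.4 names Kaplan-Meier, which ordinarily censors those deaths. On this reading the relapse share is 0.40/0.68 = 0.588, the Kaplan-Meier relapse-free estimate is 0.32^0.588 = 0.512, and the SE is sqrt(0.512² × 0.588 × 2.125/50) = 0.081. That is still above 0.071.

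**Conclusion.** The figure is wrong as printed. The maximum standard error with 50 patients is 0.071 (95% half-width 13.9 percentage points), not 0.7. This is certain for a simple proportion with all 50 patients evaluable. That the cause is a decimal slip is an inference, though a well-supported one.

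The 0.071 limit carries over to relapse if deaths without relapse are a competing event and follow-up is complete. If they are censored in a Kaplan-Meier analysis, the standard error can be somewhat higher: about 0.081 to 0.083, or roughly ±16 points, on the illustrative phase I rates, which are not planning values for this trial. The sentence should be corrected, but the effect is confined to the stated reason for the sample size.

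**What to change.** Check the source page for a lost zero. Then replace the precision clause in 12.2 with:

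> the maximum standard error will be about 0.07 (95% confidence interval about ±14 percentage points) for a simple proportion with all 50 patients evaluable; Kaplan-Meier estimates of relapse and of 2- and 5-year DFS (12.4) can have larger standard errors because of censoring.

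The cost is one sentence. The 50 patients, the accrual period, the stopping rule in 12.3 and the planned analyses stay as they are.

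### Stopping rule in section 12.3: on the exact binomial calculation 13 events in 40 already meet the >95% criterion, but the table requires 14 and no method is named

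*Combined protocol and SAP*

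**What the plan says.** Section 12.3 gives a criterion in words and then a table. In words, if at any time the rate of severe complications or of regimen-related death "exceeds 20% with a high probability (i.e. >95%) then further accrual to the trial will be terminated". The table is introduced as the consequence of that criterion: "This would occur if the following numbers of events have been observed", with "monitoring after every set of 10 patients is accrued". Its limits are 5 of 10, 8 of 20, 11 of 30 and 14 of 40.

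The section does not say whether the probability is a binomial tail, a confidence bound, an approximation or a Bayesian posterior. It gives no sidedness, no prior and no allowance for repeated looks. By contrast, section 12.4 does name a variance method for the survival estimates, where "95% confidence intervals will be calculated using" Greenwood's formula. Section 12.2 sets the trial size: "A total of 50 patients with advanced malignancies". Ten patients therefore remain to be entered after the 40-patient look.

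**The concern.** A table that is offered as the result of a probability criterion should be reproducible from it. Three of the four rows are, by the standard exact calculation. The fourth is one event higher than that calculation gives, and for a safety limit one event higher means stopping later.

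This is the only rule in the plan that ends accrual on event counts. The early rule in section 7.2.2, "If 2 of first 6 patients develop grade 3 liver or lung toxicity related to the preparative regimen", changes treatment and does not close the trial, and the same holds for the companion rule on ventilator support. With exactly 13 events in 40 patients, the worded criterion, calculated exactly, ends accrual, while the table lets the last 10 patients enter. No named method settles which of the two governs.

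**Working it through.** **Inputs (sections 12.2 and 12.3).** Reference rate 0.20. Required probability above 95%, read as one-sided because the text speaks of exceeding 20%, so the tail must be below 0.05. Looks at n = 10, 20, 30 and 40. Printed limits 5, 8, 11 and 14. Planned size 50.

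**Step 1: exact tail at each look.** For r events in n patients,

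P(X ≥ r | n, 0.20) = Σ (k = r to n) C(n,k) · 0.20^k · 0.80^(n−k).

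The limit is the smallest r for which this is below 0.05. This is the same as asking that the exact (Clopper-Pearson) one-sided 95% lower bound exceed 20%.

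| n | Printed limit | Tail at printed limit | Tail at one event fewer | Smallest qualifying count |
|---|---|---|---|---|
| 10 | 5 | 0.0328 | 0.1209 | 5 |
| 20 | 8 | 0.0321 | 0.0867 | 8 |
| 30 | 11 | 0.0256 | 0.0611 | 11 |
| 40 | 14 | 0.0194 | 0.0432 | **13** |

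The first three rows are reproduced. At n = 40 the count of 13 qualifies and 12 does not (tail 0.0875).

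**Step 2: other views of 13 in 40.** The observed proportion is 13/40 = 32.5%. The exact one-sided 95% lower bound is 20.4%. The posterior probability that the rate exceeds 20% is 97.6% with a uniform prior and 97.1% with a Jeffreys prior. All of these meet the stated level.

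**Step 3: can the printed table be recovered?** Yes, but only with something the text does not state:

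- An exact tail cut-off above 0.0328 and no higher than 0.0432 (0.04, for instance, which is 96% confidence) gives 5/8/11/14.
- A one-sided 97.5% level with a Jeffreys prior, the mid-P method or the arcsine transformation gives 5/8/11/14.
- The continuity-corrected arcsine test at one-sided 95% gives 5/8/11/14, narrowly: at 13 in 40, z = 2√40 · [arcsin√(12.5/40) − arcsin√0.20] = 1.639 against 1.645.

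**Step 4: consequence for the trial.** The probability of stopping by the fourth look comes from an exact recursion. The distribution of the event count is carried from look to look in steps of 10 patients, and the paths that have reached a limit are removed. The first three limits stay as printed. The difference between the columns is the probability of no earlier crossing and exactly 13 events at n = 40.

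| True event rate | Stopped, last limit 14 | Stopped, last limit 13 | Difference |
|---|---|---|---|
| 20% | 6.8% | 8.1% | 1.3% |
| 25% | 20.0% | 24.3% | 4.3% |
| 30% | 41.8% | 48.9% | 7.1% |
| 35% | 66.0% | 73.2% | 7.1% |
| 40% | 84.7% | 89.3% | 4.7% |

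Up to 50 − 40 = 10 further patients enter in the affected trials. Averaged over all trials at a true rate of 30% to 35%, that is about 0.071 × 10 = 0.7 patients.

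**The case against.** The best defence is that nothing in the table breaks the inequality. On exact tails the four entries carry 96.7%, 96.8%, 97.4% and 98.1%, all above 95%, and section 12.3 never says that each entry is the smallest qualifying count. A single exact cut-off at, say, 96% reproduces every row, so 14 may be deliberate. A slightly cautious last limit is also reasonable in a rule with four unadjusted looks, which already stops 6.8% of trials at a true rate of 20%. In practice those monitoring the trial will read the integers and may never see a conflict.

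Much of this stands. The entry cannot be called a proven slip, and the effect is small. What does not stand is that text and table agree. The text says accrual ends once the criterion is met, and presents the counts as the points where that happens. At 13 in 40 the criterion is met on the calculation that yields the other three rows. If a 96% or 97.5% level or an approximation was used, then the level or the method is what the text fails to state, and an edit is still needed.

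**Conclusion.** The concern holds. On the exact one-sided binomial reading at 95%, the limit at 40 patients is 13 and the printed 14 does not follow from the stated criterion. The tail probabilities are certain; the origin of 14 is not, and the documents cannot settle it.

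The size is modest. The mismatch decides the outcome only with exactly 13 events at the fourth look and no earlier crossing, at most about 7% of trials over true rates of 20% to 40%. It is still worth correcting, because it concerns the only rule that ends accrual on event counts and the repair is trivial.

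The stopping probabilities treat the events as one binomial outcome with complete follow-up at each look. That is an assumption. The text joins complications to deaths with "or regimen related mortality exceeds 20"% and does not say whether they are counted together; if they are monitored separately, the figures apply to each rate on its own.

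**What to change.** Make text and table agree in one of two ways.

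- **(a)** Change the 40-patient entry to 13 and state that the limits are the smallest counts whose exact one-sided binomial tail at a 20% rate is below 0.05. This changes one table entry and one phrase. False stopping at a true 20% rate over the four looks rises from 6.8% to 8.1%, and stopping at a true 30% rate rises from 41.8% to 48.9%.
- **(b)** If 14 is intended, keep it and replace the >95% phrase with the method and level that produced the table. This changes one phrase and leaves false stopping at 6.8%.

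Neither option needs more patients, looks or data.
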